Each number represents an enrolled patient. Circled numbers depict time at which toxicity was experienced by that patient.

between 6 and 11 of the 18 patients will be assigned the MTD.

To illustrate the method using an example, Figure 5 displays a simulation of a sample design using the method based on scenario 2 (see Table 2), where the true MTD is dose level 2. In this simulated example, the recommended dose level is 2. The first three patients are assigned to dose level 1 in weeks 1, 2, and 3. By week 4 patient 1 has a DLT and we initiate the TITE-CRM with patients 4, 5, 6, and 7 being assigned dose level 1. With no DLTs, at week 7 the dose is escalated and patients 8, 9, 10 and 11 are assigned to dose level 2. With no DLTs, by week 12 the dose is escalated again and patient 12 is assigned to dose level 3. Patient 12 has a DLT and the dose is de-escalated with patient 13 to 18 being assigned to dose level 2, with two DLTs being observed among them. The estimated MTD is dose level 2 with an estimated probability of DLT of 0.27 and 90% probability interval of (0.12, 0.44). Two of the 10 patients assigned to dose level 2 have DLTs. With an accrual rate of 4 patients per month, this study takes a total of less than 6 months to complete.

4.1.1.1 Dose Limiting Toxicities for Phase 1

All patients who receive at least one dose of cobimetinib and hydroxychloroquine, with or without atezolizumab, will be evaluable for toxicity.

In order for a patient to be evaluable for DLT assessments, the patient must either incur a DLT during the DLT evaluation period, or have received at least 80% of the planned doses of hydroxychloroquine, cobimetinib, and if applicable, atezolizumab. Patients who do not fulfill one of these criteria should be considered non-evaluable for DLT assessment purposes, and be replaced.

A DLT is defined as an AE that is possibly, probably, or definitely related to study drug administration, and that is:

- Not due to the underlying malignancy;
- Has no clear evidence of an alternative etiology; and
- Meets one of the following CTCAE v.5.0 criteria during the first 28 days of hydroxychloroquine, cobimetinib, and if applicable, atezolizumab administration:
 - Any Grade ≥ 4 hematologic toxicity, except grade 4 lymphopenia, lasting ≥ 7 consecutive days
 - Grade 3 neutropenia with fever
 - Grade 3 thrombocytopenia with clinically significant bleeding
 - Any circumstance that results in dose reduction

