4.1.1.4 Analysis of Secondary and Exploratory Endpoints

The frequency of radiographic response will be documented with summary statistics at the estimated MTD and by dose level. Best overall response rate (CR+PR) will be calculated along with a 95% confidence interval.

Progression-free survival and overall survival curves will be generated using Kaplan-Meier methodology for all patients and those assigned to the estimated MTD at the end of the trial. Treatment-related toxicity will be reported by type, frequency, and severity according to the

Columbia University Irving Medical Center
Herbert Irving Comprehensive Cancer Center
AAAS4165_Version Date: 07/07/2021

National Cancer Institute Common Terminology Criteria for Adverse Events, version 5 (NCI, 2017).

Ten paired biopsies representing combination therapy with cobimetinib and hydroxychloroquine, with and without atezolizumab, will be performed. Once adequate tissue for exploratory analysis is procured from ten subjects, subsequent subjects may not need to undergo biopsies. Necessity will be determined by the principal investigator.

Patients will be required to obtain research-specific biopsies as follows:

- Baseline biopsy of a target lesion;
- Repeat biopsy during week 3 of Cycle 1 (for pharmacodynamic analysis);
- Optional biopsy at time of progression.

All biopsies will attempt to obtain 4-6 cores. Each core biopsy obtained from a patient will only be performed if deemed safe by the interventional radiologist. The interventional radiologist will cease from obtaining biopsies if he/she deems that additional biopsies performed from pulmonary nodules would put the patient at significant increased risk for biopsy-related complications, in which case the core biopsies should be limited to 3 cores, if feasible. Two of the cores will be processed for formalin fixation, 2 will be frozen in liquid nitrogen, and if additional core tissue is available, samples will be processed for generation of organoids and/or single cell DNA analysis for exploratory studies.

Changes in CD8⁺ T-cells, FoxP3⁺ T-reg, autophagy and other markers from pre-treatment biopsies at baseline to on-treatment biopsies will be summarized and reported as means, medians, standard deviations, and ranges, and compared using the Wilcoxon signed rank test for patients assigned to the MTD. These correlative studies will be considered exploratory in nature.

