9.3 Relationship to Study Intervention

All AEs and SAEs, whether volunteered by the patient, discovered by study personnel during questioning, or detected through physical examination, laboratory test, or other means, will be reported appropriately. Each reported AE or SAE will be described by its duration (i.e., start and

Columbia University Irving Medical Center
Herbert Irving Comprehensive Cancer Center
AAAS4165_Version Date: 07/07/2021

end dates), regulatory seriousness criteria if applicable, suspected relationship to atezolizumab and/or cobimetinib (see following guidance), and actions taken.

To ensure consistency of AE and SAE causality assessments, investigators should apply the following general guideline:

Yes

There is a plausible temporal relationship between the onset of the AE and administration of cobimetinib and hydroxychloroquine either alone or with atezolizumab, and the AE cannot be readily explained by the patient's clinical state, intercurrent illness, or concomitant therapies; and/or the AE follows a known pattern of response to the study drug; and/or the AE abates or resolves upon discontinuation of the study drug or dose reduction and, if applicable, reappears upon re-challenge.

No

Evidence exists that the AE has an etiology other than that from cobimetinib and hydroxychloroquine, either alone or with atezolizumab (e.g., preexisting medical condition, underlying disease, intercurrent illness, or concomitant medication); and/or the AE has no plausible temporal relationship to the administration of the study drugs (e.g., cancer diagnosed 2 days after first dose of study drug).

Expectedness

Expected adverse reactions are AEs that are known to occur for the study intervention being studied and should be collected in a standard, systematic format using a grading scale based on functional assessment or magnitude of reaction. Identify the source of the reference safety information used to determine the expectedness of the AE (e.g., IB, approved labeling). Expectedness is assessed based on the awareness of AEs previously observed, not on the basis of what might be anticipated from the properties of the study intervention.

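### The DLT definition and the general causality guidance set different relatedness tests, so one event can pass the DLT test yet be recorded as unrelated and drop out of the safety summary

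*Combined protocol and SAP*

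**What the plan says.** **DLT definition (4.1.1.1).** "A DLT is defined as an AE that is possibly, probably, or definitely related to study drug administration". The event must also not be due to the malignancy, and a further condition reads: "Has no clear evidence of an alternative etiology". The window is "during the first 28 days of hydroxychloroquine, cobimetinib, and if applicable, atezolizumab administration", so all three drugs are covered. The same section says that final DLT decisions are made in consultation with the Principal Investigator. It also requires DLTs to be reported to the lead site by signed memo within 24 hours and entered in the trial database.

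**General causality guidance (9.3).** Each adverse event is to be described by, among other things, its "suspected relationship to atezolizumab and/or cobimetinib (see following guidance), and actions taken". The guidance that follows has two categories.

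- Yes opens: "There is a plausible temporal relationship between the onset of the AE and administration of cobimetinib and hydroxychloroquine either alone or with atezolizumab", and continues: "and the AE cannot be readily explained by the patient's clinical state, intercurrent illness, or concomitant therapies". Further routes, joined by and/or, are a known response pattern and improvement on stopping or reducing the drug.
- No applies when there is evidence of a cause other than the study drugs, or when the timing is implausible. This definition also names hydroxychloroquine.

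**Safety summary (4.1.1.4).** "Treatment-related toxicity will be reported by type, frequency, and severity according to the" NCI toxicity criteria, version 5. No table of adverse events regardless of attribution is planned there.

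**The concern.** The DLT definition relies on three positive grades of relatedness. The plan defines none of them, and its general causality guidance has no place for them. The two sections also differ on how much evidence of another cause removes an event: clear evidence in 4.1.1.1, any evidence in 9.3. An investigator who follows both can reach different answers for the same event.

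Two things are at stake. The first is the safety profile, which is the phase 1 secondary objective. The trial has no control arm, and the only planned toxicity summary is filtered by an attribution that may be stricter than the one used for DLTs. The second is the DLT count itself, if the Yes/No judgement influences which events are put forward as DLTs.

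**Working it through.** No stated figure is in dispute, so the main check is a comparison of the two tests. Take an event with plausible timing that meets a severity criterion in 4.1.1.1, is judged at least possibly related, and is not due to the malignancy.

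| Evidence on cause | DLT relatedness test (4.1.1.1) | Guidance in 9.3 |
|---|---|---|
| No other ready explanation | Met | Yes |
| Some but not clear evidence of another cause, enough to explain the event readily; no known pattern, no information from stopping the drug | Met | Yes fails; No is met |
| Same, but the event follows a known pattern | Met | Yes and No can both be argued |
| Readily explained otherwise, but no actual evidence of that cause | Met | First route to Yes fails and No is not met; undefined unless another route to Yes applies |
| Clear evidence of another cause | Not met | No is met |

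The sections agree in the first row and generally in the last. In the second row they contradict each other: the event is related enough to be a DLT but is recorded as unrelated. In the third and fourth rows 9.3 gives no unique answer.

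**Drugs covered.** The 9.3 lead-in names atezolizumab and/or cobimetinib. Both category definitions below it name cobimetinib and hydroxychloroquine, with or without atezolizumab. The section is therefore inconsistent within itself.

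**Scale of one event.** Section 4.1.1 expects 6 to 11 of 18 patients at the MTD, and 4.1.1.3 reports the observed DLT rate by dose level. One reclassified event changes that rate at the MTD by 1/11 = 9.1 to 1/6 = 16.7 percentage points.

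**If DLTs were lost (assumption, not in the documents).** Suppose a share m of true DLTs goes unrecorded. The apparent rate is then 0.30 × (1 − m), and the true rate that looks on target is 0.30/(1 − m).

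- m = 10%: 0.30 × 0.9 = 0.27; 0.30/0.9 = 0.333.
- m = 20%: 0.30 × 0.8 = 0.24; 0.30/0.8 = 0.375.

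**Illustrative simulation.** A two-stage TITE-CRM was simulated with the plan's empirical model, prior variance 1.34, N = 18, 4-week window, one patient per week and target 0.30, in 1,000 runs per setting. The plan gives no skeleton, so one was assumed (half-width 0.07, prior MTD at level 2).

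With no loss, correct selection was 74%, 55% and 77% in scenarios 1 to 3, against 74%, 53% and 74% in Table 2. Patient allocation matched less well: about 4/5/9 against 2/5/11 in scenario 3. This is not a reproduction of Table 2.

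The probability of selecting a level above the true MTD was:

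| Share of DLTs unrecorded (assumed) | Scenario 1 (levels 2 + 3) | Scenario 2 (level 3) |
|---|---|---|
| 0% | 22.7 + 3.1 = 25.8% | 26.4% |
| 10% | 30.4 + 7.3 = 37.7% | 35.9% |
| 20% | 39.6 + 13.6 = 53.2% | 46.9% |

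The Monte Carlo standard error is at most √(0.25/1000) = 1.6 points. In scenario 3 the top level is the MTD, so no higher level can be chosen. The table shows direction and sensitivity only. Nothing in the plan says what share, if any, would be lost.

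**The case against.** A reader might infer four stronger things. The documents support none of them.

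- *Hydroxychloroquine toxicity is excluded from causality assessment.* The lead-in omits the drug, but it points to guidance whose Yes and No definitions both include it. Section 9.4.5.3 also speaks of events possibly related to the combination that includes it. The defect is one incomplete sentence.
- *The two sections put the burden of proof in opposite directions.* Only the first route to Yes is stricter. The and/or routes widen Yes, and No does require evidence of another cause, as the DLT rule does. The difference is one of threshold: any evidence against clear evidence.
- *The primary endpoint cannot be derived.* The plan nowhere says that DLTs are computed from the Yes/No judgement. They have their own criteria, consultation with the Principal Investigator and a 24-hour memo, and 13.5 requires quarterly source verification of DLT data. The case report forms are not in the documents, so how attribution is stored cannot be seen.
- *DLTs will be missed and the MTD set too high.* With separate adjudication, a No under 9.3 does not by itself remove a DLT.

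These answers stand, and they limit the concern. They do not remove it. Consultation and the memo supply no scale for the three grades of relatedness, and the memo starts only once someone has judged the event to be a DLT. Nor does separate DLT adjudication restore events to the treatment-related summary. The underlying adverse-event data are not lost: 9.1.1 records severity regardless of relationship to study medication. That makes the reporting gap easy to close.

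**Conclusion.** The point holds as an inconsistency between 4.1.1.1 and 9.3. The same event can meet the DLT relatedness test and be recorded as unrelated, and it would then be absent from the only toxicity summary planned in 4.1.1.4. The 9.3 lead-in is also inconsistent with its own definitions about hydroxychloroquine.

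The conflict rests on the text alone. The step to the safety summary assumes that treatment-related there means Yes under 9.3, since the plan gives no other definition. An effect on the MTD needs the further assumption that the 9.3 judgement influences which events are put forward as DLTs. The 10% and 20% losses have no source in the documents, so an upward shift of the MTD remains a possible risk of unknown size. The change is worth making because it protects the primary endpoint and the safety objective at very low cost.

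**What to change.** 1. Reconcile 4.1.1.1 and 9.3 on one relatedness threshold. Either use a common scale in both, or add a sentence stating that possible or higher counts as Yes and meets the DLT relatedness test. Settle in the same place whether evidence of another cause must be clear before an event is recorded as No, and use that threshold for the treatment-related table.
2. Add hydroxychloroquine to the 9.3 lead-in.
3. In 4.1.1.4, report all adverse events regardless of attribution, by dose level, beside the treatment-related table.

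Attribution drug by drug on a five-level scale would be a preference. It is not needed here, because the DLT definition asks about study drug administration as a whole.

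Cost: a few sentences and one extra table from data already collected. There is no change to sample size, dosing or visits.

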| Objectives | 
PRIMARY OBJECTIVES
 
Phase 1: To estimate the maximum tolerated dose of cobimetinib, atezolizumab, and hydroxychloroquine in KRAS-mutated advanced malignancies.
 
Phase 2: To evaluate the preliminary efficacy based on the objective response by 16 weeks of the combination of cobimetinib, atezolizumab, and hydroxychloroquine in KRAS-mutated advanced malignancies.
 
SECONDARY OBJECTIVES
 
Phase 1: To evaluate the safety profile of the combination of cobimetinib, atezolizumab, and hydroxychloroquine in KRAS-mutated advanced malignancies.
 
Phase 2: To evaluate the progression free and overall survival, and the safety profile of cobimetinib, atezolizumab, and hydroxychloroquine combined treatment in KRAS-mutated advanced malignancies.
 
Exploratory Objectives
 
Determine MEK and autophagy pathway inhibition, and CD8+ T-cell infiltration within tumor specimens.Perform RNA seq analysis within tumor specimens. |

Columbia University Irving Medical Center
Herbert Irving Comprehensive Cancer Center
AAAS4165_Version Date: 07/07/2021

| | |
|--|--|
| Number of Subjects | 
Phase 1: KRAS-mutated histology (N=18)
 
Phase 2: KRAS-mutated histology pending results of phase 1
 
Cohort 1 – Advanced Pancreas Adenocarcinoma (N = 23-67)
 
Cohort 2 – Advanced Colorectal Adenocarcinoma (N = 20-34)
 
Cohort 3 – Histology Agnostic Adenocarcinoma (N = 23-56)
 |
| Study Product, Dose, Route, Regimen | 
Dose Level 1: Cobimetinib (40mg) orally once daily (morning) on days 1-21 of each 28-day; Hydroxychloroquine (600mg) orally twice daily on days 1-28 of each 28-day cycle
 
Dose Level 2: Cobimetinib (40mg) orally once daily (morning) on days 1-21 of each 28-day; Hydroxychloroquine (600mg) orally twice daily on days 1-28 of each 28-day cycle; Atezolizumab 840 mg IV on Days 1 and 15 of each cycle
 
Dose Level 3: Cobimetinib (60mg) orally once daily (morning) on days 1-21 of each 28-day; Hydroxychloroquine (600mg) orally twice daily on days 1-28 of each 28-day cycle; Atezolizumab 840 mg IV on Days 1 and 15 of each cycle 28 day cycle.
 |
| Duration of administration | Continuous 28-day cycle |
| Reference therapy | N/A |
| Statistical Methodology | The MTD will be estimated using the time to event continual reassessment method (TITE-CRM). The MTD is defined as the dose combination at which 30% of the patients experience DLT by the end of Cycle 2. |

Protocol Schema:

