of 18. The prior distribution of the model parameter is assumed to be normal with a mean of 0 and a variance of 1.34. The dose-toxicity model is calibrated such that the eventual dose yields between 18% and 32% DLT (Cheung & Chappell, 2002; Lee & Ying Kuen, 2009) and good operating characteristics across a wide range of potential scenarios of toxicity profiles. Given that the majority of the toxicities for the cobimetinib and atezolizumab trial occurred in the first cycle of treatment, the proposed toxicity evaluation period is 4 weeks. In the first stage, each cohort will be followed for the entire 4 weeks in the absence of a DLT. Once a DLT is observed, we will impose a minimum of 1 week of observation between patients in the second stage of the design. We do not allow for dose skipping during dose escalation or escalation immediately after a dose limiting toxicity. **Patients who do not complete 80% of dosing due to reasons other than treatment-related toxicity (e.g. non-compliance) will need to be replaced. Moreover, patients who discontinue due to reasons other than treatment-related toxicity (i.e. progression or death) prior to completing 4 weeks of therapy without having experienced a DLT will be considered not evaluable and be replaced.** Partial toxicity information from subjects that are greater than 80% compliant may be included for dose assignments and will continue to be used for future dose assignments unless the patient is not evaluable and/or discontinues prior to the 4 week DLT evaluation. To evaluate the performance of the method, 2000 simulations under these scenarios of toxicity profiles were done. The operating characteristics of our design under these scenarios are displayed in Table 2. Based on these simulation results, the 18-patient design selects the correct MTD with probabilities over 53% under all possible scenarios. These simulations assume that the patients arrive at a rate of 4 patients every 4 weeks (i.e., a patient every week) which is our full toxicity evaluation window, and that a DLT occurs randomly and uniformly

Columbia University Irving Medical Center
Herbert Irving Comprehensive Cancer Center
AAAS4165_Version Date: 07/07/2021

within the observation window. Moreover, based on the various simulation scenarios, we expect

[figure not shown]

Figure 5. Simulated trial using time-to-event continuous reassessment method.

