 - Any Grade ≥ 3 non-hematologic toxicity except:
 - Nausea, vomiting, and/or diarrhea of Grade 3 severity that resolves within 7 consecutive days with optimal prophylaxis and/or treatment;
 - Grade 3 fatigue that resolves to Grade ≤ 2 within 7 consecutive days;
 - Grade ≥ 3 alkaline phosphatase that is related to underlying malignancy (eg, bone metastasis).
 - Grade ≥ 3 asymptomatic or mildly symptomatic rash will not be considered a DLT if the event can be adequately managed with supportive care, the event resolves to become asymptomatic and/or Grade ≤ 2 within 7 days, or the event continues for longer than 7 days in a patient who has not received appropriate supportive therapy.
 - Grade ≥ 3 elevation of serum creatine phosphokinase (CPK) level will not be considered a DLT if the event is asymptomatic (i.e., not accompanied by signs, symptoms, or other laboratory abnormalities associated with rhabdomyolysis or myocardial injury) and is deemed by the investigator to be clinically insignificant.
 - Grade 3 arthralgia will not be considered a DLT if the event can be adequately managed with supportive care or the event resolves to Grade ≤ 2 within 7 days.
 - Grade 3 fever (in the absence of any clinically significant source of fever) will not be considered a DLT if the event resolves to Grade ≤ 2 within 7 days or the event continues for longer than 7 days in a patient who has not received appropriate supportive care.

- Grade 3 laboratory abnormality will not be considered a DLT if the event is asymptomatic and is deemed by the investigator to be clinically insignificant.
- Grade 3 autoimmune thyroiditis or other endocrine abnormality will not be considered a DLT if the event can be managed by endocrine therapy that would not necessitate initiation of systemic corticosteroids.
- Grade ≥ 3 total bilirubin that is not attributed to disease progression
- Grade ≥ 3 AST or ALT, but not isolated elevation in ALT (non-specific) in subjects without metastatic disease in the liver
- AST or ALT $\geq 10X$ ULN in subjects with liver metastasis
- QTc interval ≥ 501 ms confirmed by a repeat ECG
- Grade ≥ 3 Creatine Kinase with symptoms of myalgia
- Grade ≥ 2 retinal events lasting greater than 14 days or Grade ≥ 3 retinal events that are confirmed by ophthalmologic examination
- Grade ≥ 3 rash that persists despite optimal treatment, and that does not resolve to Grade ≤ 2 within 7 days.

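### The DLT definition ties the 28-day limit to meeting the criterion, so late-starting Grade 4 hematologic and Grade 2 retinal events cannot complete their required duration and go uncounted

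*Combined protocol and SAP*

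**What the plan says.** Section 4.1.1.1 requires that a related event "Meets one of the following CTCAE v.5.0 criteria during the first 28 days of hydroxychloroquine, cobimetinib, and if applicable, atezolizumab administration". The limit applies to meeting the criterion; onset is not mentioned. Among the criteria that follow are:

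- Grade 4 or higher "hematologic toxicity, except grade 4 lymphopenia, lasting" at least 7 consecutive days;
- Grade 2 or higher "retinal events lasting greater than 14 days", or Grade 3 or higher retinal events with no duration attached, so only Grade 2 depends on duration;
- Grade 3 or higher "rash that persists despite optimal treatment, and that does not resolve to Grade" 2 or lower within 7 days.

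In Section 4.1.1, Phase I Statistical Considerations, "the proposed toxicity evaluation period is 4 weeks", and the simulations behind Table 2 assume "that a DLT occurs randomly and uniformly" within the observation window. The synopsis has a different window: its MTD is the combination at which 30% of patients "experience DLT by the end of Cycle 2". No section says how to score an event that is still running on Day 28, and no TITE-CRM weight function is given.

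**The concern.** DLT is the Phase 1 primary endpoint and the only outcome that drives dose assignment. If a criterion needs 7 or 15 days to be fulfilled and must be fulfilled by Day 28, the same toxicity counts when it starts early and not when it starts late. The loss runs one way, towards fewer DLTs. In the first stage, a cohort with such an event running at week 4 would look free of DLTs. In the second stage, the patient's follow-up would look complete and uneventful. Both favor a higher dose. Table 2 makes no allowance for this.

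**Working it through.** **1. Onset days that cannot qualify.** Last qualifying onset day = 28 - required days + 1.

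- Hematologic, 7 days: 28 - 7 + 1 = Day 22. Days 23-28 are lost: 6/28 = 21.4%.
- Grade 2 retinal, more than 14 days (15 calendar days): 28 - 15 + 1 = Day 14. Days 15-28 are lost: 14/28 = 50%. Table 10, footnote 9 schedules no eye examination between screening and Cycle 3 Day 1, so few such events would be documented in the window anyway.
- With the synopsis window of 56 days the shares would be 6/56 = 10.7% and 14/56 = 25%.

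**2. What happens to the patient.** Section 4.1.1.1 makes a patient without a DLT evaluable at 80% or more of planned doses of each drug. Table 4 gives hydroxychloroquine on Days 1-28, cobimetinib on Days 1-21 and any atezolizumab on Days 1 and 15. Suppose all drugs are held from onset:

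- Onset Day 24: hydroxychloroquine 23/28 = 82.1%, cobimetinib 21/21, atezolizumab complete. The patient is an evaluable non-DLT. The same holds for Days 25-28, so for five of the six lost hematologic days.
- Onset Day 23: 22/28 = 78.6%. Section 4.1.1.1 replaces the patient. Phase I Statistical Considerations replaces only when the shortfall is not due to treatment-related toxicity, so the two rules disagree.
- A Grade 2 retinal event with onset on Days 15-23 and hydroxychloroquine held also falls below 80%.

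**3. Items that do not lose events.** The 7-day clauses for Grade 3 nausea, vomiting, diarrhea and fatigue are exemptions from a general Grade 3 rule. A late unresolved event is a DLT by default, but one starting after about Day 22 cannot be finally classified by Day 28. Symptomatic Grade 3 or higher rash is already a DLT under the general rule.

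**4. Reproducing Table 2.** A two-stage TITE-CRM was simulated with the stated inputs: empirical model, prior N(0, 1.34), target 0.30, N = 18, cohorts of three, one arrival per week, no skipping, no escalation right after a DLT. The skeleton is not given; 0.169/0.300/0.443 was assumed (prior MTD at level 2, half-width 0.07 from the 18%-32% interval), with linear weights. Correct selection over runs of 800 and 2,000 trials was 72.4-74.6% in Scenario 1 (stated 74%) and 53.0-53.8% in Scenario 2 (stated 53%). Scenario 3 gave 77.6% (stated 74%; 800 runs). The average numbers assigned do not match: in Scenario 1, 13.1/4.0/0.9 against 11/4/3.

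**5. Effect of the loss.** Let f be the share of DLTs carrying the 7-day clause (an assumption). Scored rate at a true 30% = 0.30 × (1 - f × 6/28). Lost events are entered as completed non-DLTs; 2,000 runs per cell.

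| f | Scored rate | Scenario 1 correct | Scenario 2 correct | Scenario 2 selects level 3 (true 45%) |
|---|---|---|---|---|
| 0 | 30.0% | 72.4% | 53.0% | 26.0% |
| 10% | 29.4% | 69.4% | 51.8% | 28.0% |
| 25% | 28.4% | 65.8% | 51.0% | 30.9% |
| 50% | 26.8% | 58.8% | 49.6% | 36.5% |
| 100% | 23.6% | 43.8% | 42.8% | 47.8% |

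Simulation error on one cell near 72% is about √(0.72 × 0.28/2000) = 1.0 point, so the 3-point fall at f = 10% is only about two standard errors of a difference. If instead 10% of DLTs carried the 14-day clause, Scenario 1 correct selection would be 65.7%. If lost patients were replaced rather than scored, the rate at f = 100% would be 0.2357/(1 - 0.30 × 6/28) = 25.2% instead of 23.6%: smaller, same direction.

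**The case against.** A reader might infer that any event starting late in the window can never be a DLT. The documents do not support that. Neutropenia with fever, thrombocytopenia with bleeding, bilirubin, AST/ALT, QTc, creatine kinase with myalgia, Grade 3 or higher retinal events and general Grade 3 non-hematologic toxicity carry no qualifying duration, and the gastrointestinal and fatigue clauses work the other way. Nor does the plan state that a lost event is scored as a full-weight non-DLT. That follows from the 4-week evaluation period and the 80% rule, for patients who reach 80%.

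The wording can also be read as referring to onset, and Section 4.1.1.1 leaves final determinations to consultation with the Principal Investigator. That names who decides but gives no scoring rule. The criterion covering any circumstance that leads to a dose reduction might catch some events. However, Section 8.1 bars reductions in the DLT period unless a DLT is already confirmed, and a reduction made in Cycle 2 falls after Day 28. It is not a dependable backstop.

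The best remaining objection is that the MTD targets DLT as defined, and Table 2 may already use rates so defined. On that view nothing is mis-simulated, but the 30% target then refers to a narrower event than severe toxicity beginning in the window. Uniform timing would also fail for this class, since a 7-day criterion cannot be met before Day 7.

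**Conclusion.** The concern holds for two criteria: Grade 4 or higher hematologic toxicity (21% of onset days lost) and Grade 2 retinal events (50%, with little practical weight given the eye examination schedule). The direction, too few DLTs and a higher selected dose, is clear on the plain wording, relative to a count of qualifying toxicities that begin in the window.

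The size is not established. It rests on uniform onset, an assumed skeleton that matches Table 2 only in part, and a share of duration-based DLTs that the documents do not give. Because only two criteria are affected, the low end is more plausible: about 3 points of correct selection in Scenario 1 at a 10% share. The larger falls need shares of 50% or more, which nothing in the documents supports. The point still merits a change before enrollment because it concerns the definition of the primary endpoint and costs almost nothing to correct.

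**What to change.** In Section 4.1.1.1, state that duration-based criteria are judged by onset within the DLT evaluation window, and that an event ongoing at Day 28 is followed until its duration, or the resolution that would exempt it, is known. In Phase I Statistical Considerations, state the weight function. State also that such a patient stays pending until then: not entered as a full-weight non-DLT, and not used to support escalation in either stage. With onset counting nothing is truncated, and the f = 0 row of the table applies (about 72% and 53%), apart from the short delay, which was not simulated.

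Three sets of passages must also be reconciled:

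- the replacement rules in Section 4.1.1.1 and Phase I Statistical Considerations, together with the 90% figure for dose interruptions in Section 8.1;
- the synopsis window (end of Cycle 2) and the 28 days;
- the retinal criterion and the examination schedule in Table 10.

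The cost is a few sentences and a delay of up to 7-14 days in classifying a few patients: an event starting on Day 28 reaches its 7th day on Day 34 and its 15th day on Day 42.
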